7.5.12. Reporting SAEs

Prompt notification by the investigator to the Sponsor of an SAE is essential so that legal obligations and ethical responsibilities toward the safety of participants and the safety of a study intervention under clinical investigation are met.

Any AE considered serious by the investigator or that meets SAE criteria ([Section 7.5.2](#)) must be reported to the Sponsor immediately (within 24 hours of becoming aware of the SAE); these include anaphylaxis and confirmed organ transplant rejection. The investigator will assess whether there is a reasonable possibility that the vaccine caused the SAE. The Sponsor will be responsible for notifying the relevant regulatory authorities of any SAE as outlined in the 21 US CFR Parts 312 and 320. The investigator is responsible for notifying the institutional review board (IRB) directly.

If the eCRF is unavailable at the time of the SAE, the following contact information is to be used for SAE reporting:

- SAE Mailbox: [contact]
- SAE Hotline (USA): [contact]
- SAE Fax line (USA): [contact]

Regulatory reporting requirements for SAEs are described in [Section 7.5.16](#).

The investigator and any qualified designees are responsible for detecting, documenting, and recording events that meet the definition of an AE, including SAEs, and remain responsible for following up AEs that are serious, considered related to vaccine or study procedures, or that caused the participant to discontinue the study.

7.5.13. Time Period and Frequency for Collecting AE and SAE Information

Medical occurrences that begin before the start of vaccine dosing but after obtaining informed consent will be recorded in the Medical History/Current Medical Conditions section of the eCRF and not in the AE section; however, if the condition worsens at any time during the study, it will be recorded and reported as an AE.

Adverse events may be collected as follows:

- Observing the participant
- Receiving an unsolicited complaint from the participant
- Questioning the participant in an unbiased and nonleading manner

Solicited ARs will be collected from the day of injection through 6 days after each dose. Other (unsolicited) AEs will be collected from the day of injection through 28 days after each dose.

SAEs will be collected from the start of vaccine dosing until the last day of study participation.

All SAEs will be recorded and reported to the Sponsor or designee immediately and in all circumstances within 24 hours. The investigator will submit any updated SAE data to the Sponsor within 24 hours of it being available.

An abnormal value or result from a clinical or laboratory evaluation can also indicate an AE if it is determined by the investigator to be clinically significant (eg, leads to dose modification or study drug discontinuation, or meets any serious criteria). If this is the case, it must be recorded in the source document and as an AE on the appropriate AE form(s). The evaluation that produced the value or result should be repeated until that value or result returns to normal or is stabilized and the participant's safety is not at risk.

Investigators are not obligated to actively seek AEs or SAEs after EOS participation. However, if the investigator learns of any SAE (including a death) at any time after a participant has withdrawn from or completed the study, and the investigator considers the event to be reasonably related to the vaccine or study participation, the investigator must promptly notify the Sponsor.

7.5.14. Method of Detecting AEs and SAEs

Electronic diaries have specifically been designed for this study by the Sponsor. The diaries will include prelisted AEs (solicited ARs) and severity scales; they will also include blank space for the recording of information on other AEs (unsolicited AEs) and concomitant medications/vaccinations.

The investigator is responsible for the documentation of AEs regardless of suspected causal relationship to vaccine. For all AEs, the investigator must pursue and obtain information adequate to determine the outcome of the AE and to assess whether the AE meets the criteria for classification as an SAE requiring immediate notification to the Sponsor or its designated representative.

Care will be taken not to introduce bias when detecting AEs and/or SAEs. Open-ended and nonleading verbal questioning of the participant is the preferred method to inquire about the occurrence of AEs.

7.5.15. Follow-up of AEs and SAEs

After the initial AE/SAE report, the investigator is required to proactively follow each participant at subsequent visits and contacts.

All AEs and SAEs will be treated as medically appropriate and followed until resolution, stabilization, the event is otherwise explained, or the participant is LTFU, as defined in [Section 6.4](#), including ongoing SAEs after study completion.

7.5.16. Regulatory Reporting Requirements for SAEs

- Prompt notification by the investigator to the Sponsor of a SAE is essential so that legal obligations and ethical responsibilities toward the safety of participants and the safety of a study intervention under clinical investigation are met.
- The Sponsor has a legal responsibility to notify both the local regulatory authority and other regulatory agencies about the safety of a study intervention under clinical investigation. The Sponsor will comply with country-specific regulatory requirements relating to safety reporting to the regulatory authority, IRBs, and investigators.
- Investigator safety reports must be prepared for suspected unexpected serious ARs according to local regulatory requirements and Sponsor policy and forwarded to investigators as necessary.
- An investigator who receives an investigator safety report describing an SAE or other specific safety information (eg, summary or listing of SAEs) from the Sponsor will review and then file it along with the IB and will notify the IRB, if appropriate according to local requirements.

7.6. Safety Monitoring

The CRO's medical monitor, the Sponsor's medical monitor, and the individual study site investigator(s) will monitor safety throughout the study.

7.6.1. Safety Review Committee

An independent safety review committee (SRC) consisting of transplant nephrologist(s) and hepatologist(s) not involved in the conduct of the study will monitor and adjudicate for events of organ transplant rejection starting from Day 1 and throughout the study period. The SRC will operate under the rules of an approved charter that will be written and reviewed at the organizational meeting of the SRC. Details regarding the SRC composition, responsibilities, procedures, and frequency of data review will be defined in its charter.

In Part A, the investigator will review laboratory safety assessments of kidney and liver function performed as part of the study at Day 1, Day 8, Day 29, Day 36, and Day 57 for unvaccinated SOT recipients who receive 2 doses (Group A1) and on additional Days 85, 92, and 113 for unvaccinated SOT recipients who receive 3 doses (Group A2), and at Day 1 (dose 3), Day 8, and Day 29 for previously vaccinated SOT recipients (Group A3), for close monitoring around the time of vaccination. In Part B, the investigator will review laboratory safety assessments of kidney and liver function performed as part of the study at BD-D1, BD-D8, and BD-D29. If any of the following criteria are met, the laboratory test(s) must be repeated within 3 days: an increase in serum creatinine $\geq 25\%$ from baseline or increase in UPCR > 0.5 g/g from baseline in kidney SOT

recipients, and an increase in ALT or AST $> 3x$ the baseline in liver SOT recipients. Additional tests may be performed at the discretion of the investigator upon approval of the Sponsor. The investigator should perform a clinical assessment (eg, elicit a history/narrative of the event, perform a physical examination, request diagnostic tests such as imaging or biopsy) of any laboratory abnormality if there is suspicion of an organ transplant rejection. Clinical referral to a transplant specialist for further assessment may be performed by the investigator if needed. A confirmed diagnosis of organ transplant rejection will be based on histologic assessment or tissue biopsy. After Day 57 (unvaccinated SOT recipients who receive 2 doses [Group A1]), after Day 113 (unvaccinated SOT recipients who receive 3 doses [Group A2]), or after Day 29 (previously vaccinated SOT recipients who receive dose 3 [Group A3]) in Part A, or after BD-D29 in Part B Booster Phase, the investigator will review standard-of-care laboratory assessments and report any suspected or confirmed event of organ transplant rejection until the EOS. The investigator or designee is responsible for reporting to the Sponsor, via the EDC system within 24 hours of observation and subsequently routed to SRC for independent review, if any of the following is met:

1. Any of the thresholds for kidney or liver function test is met, confirmed by repeat test, and clinically assessed as suggestive of organ transplant rejection,
2. Any suspected event of organ transplant rejection based on clinically significant kidney or liver function test(s) associated with signs and symptoms suggestive of transplant rejection, or
3. Any report of biopsy-proven organ transplant rejection.

The SRC will assess if the event is a true case of organ transplant rejection. The Sponsor will then make a final decision on whether to suspend further enrollment and/or study dosing based on assessment of the overall potential safety risk to study participants or potential participants who have undergone SOT.

7.6.2. Internal Safety Committee and Study Pause Rules

An internal safety team (IST) will be created specifically to review safety and reactogenicity data after:

- At least 10 SOT recipients have received their third dose of study vaccine and have at least 7 days of reactogenicity data
- At least 55 SOT recipients have received their third dose of study vaccine, unless a safety event requires earlier review
- Any other ad hoc safety concerns based on ongoing safety surveillance

The IST will operate under the rules of an approved charter that will be written and reviewed at the organizational meeting of the IST. Details regarding the IST composition, responsibilities, procedures, and frequency of data review will be defined in its charter.

Study pause rules will be implemented and will only remain in effect until all study participants who consented to receive a third dose have received their third dose of vaccine. If the following occur, vaccination with third dose may be temporarily suspended until expedited Sponsor review of safety data take place to assess over all potential safety risk to SOT recipients:

- Reactogenicity: Two Grade 4 solicited local or systemic reactogenicities that are related to the vaccine
- Hypersensitivity: Five SOT recipients experiencing a severe systemic allergic reaction that is related to the vaccine
- Adverse Event: Three SAEs or Grade 4 AEs (laboratory and vital sign abnormalities per [Section 10.4](#), Appendix 4 reported as AEs by the investigator) that are related to the vaccine
- Fatal Outcome: One death that is related to the vaccine

The investigators, study medical monitor, and Sponsor will monitor for events that could trigger a study pause. The investigator or designee is responsible for reporting to the Sponsor, via the EDC system within 24 hours of observation, each event potentially meeting any pause rule criterion.

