Section 2. Objectives and Endpoints	Added objectives for the addition of Part B.	To add a new study part (Part B) to continue to evaluate the benefit-risk profile of a booster dose of mRNA-1273.
Section 1.3.3. Overall Benefit/Risk Conclusion, Section 3.1. General Design, Section 3.1.1. Study Periods, Section 3.1.1.2. Treatment Period and Follow-up Period, Section 3.2. Scientific Rationale for Study Design, Section 3.3. Justification for Dose and Choice of Study Population, Section 4.2. Study Eligibility Criteria (Part B), Section 5.2. Randomization and Stratification, Section 5.3.2. Administration of Study Vaccine, Section 7.1. Safety Assessments and Procedures, Section 7.1.2. Safety Telephone Calls, Section 7.1.3. Safety Laboratory Assessments. Section 7.4. Exploratory Assessments, Section 7.6.1. Safety Review Committee, Section 8.1. Sample Size, Section 8.3.3.	Part B is being added to Study mRNA-1273-P304	To add a new study part (Part B) to continue to evaluate the benefit-risk profile of a booster dose of mRNA-1273.

Section # and Name	Description of Change	Brief Rationale
Immunogenicity Analyses, Section 8.4.1. Interim Analyses, APPENDIX 1: Schedule of Events, Table 10		
Section 3.1. General Design	Added a statement that the Part B Booster Phase may test or replace the prototype 100 µg booster dose with a variant-specific mRNA-1273 vaccine.	To allow for flexibility in the protocol in case data show a decreased immune response.
Section 3.1.1. Study Periods	Added dose delay information for Part A.	To provide guidance to the investigators if the last dose is delayed.
Section 3.2. Scientific Rational for Study Design	Added Study mRNA-1273-P205.	To provide support of the booster dose.
Section 3.3. Justification for Dose and Choice of Study Population	Added Study mRNA-1273-P205.	To provide support of the booster dose.
Section 4.1.1.1. Inclusion Criteria for Transplant Recipients: Inclusion Criterion 1	Modified the time interval requirement between informed consent and date of transplant from 6 months to 90 days.	To provide opportunity for sites to enroll transplant recipients who are clinically eligible to receive the COVID-19 vaccine outside of the study.

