The CEAC will operate under the rules of an approved charter that will be written and reviewed at the organizational meeting of the CEAC. Details regarding the CEAC composition, responsibilities, procedures, and frequency of data review will be defined in its charter.

In addition, an Internal Safety Team (IST) will be created specifically to review safety and reactogenicity data after:

- At least 10 SOT recipients have received their third dose of study vaccine (Group A2 and Group A3) and have at least 7 days of reactogenicity data
- At least 55 SOT recipients have received their third dose of study vaccine (Group A2 and Group A3), unless a safety event requires earlier review
- Any other ad hoc safety concerns based on ongoing safety surveillance

The IST will operate under the rules of an approved charter that will be written and reviewed at the organizational meeting of the IST. Details regarding the IST composition, responsibilities, procedures, and frequency of data review will be defined in its charter.

Study Duration:

Part A:

Per participant receiving 2 vaccine doses (Group A1), the study duration will be approximately 13 months, which includes 1 week for screening, 1 month for dosing, and 12 months of follow-up after the second dose to monitor for safety, immunogenicity, and breakthrough SARS-CoV-2 infection or COVID-19.

Per participant receiving 3 vaccine doses (Group A2), the study duration will be approximately 15 months, which includes 1 week for screening, 3 months for dosing, and 12 months of follow-up after the third dose to monitor for safety, immunogenicity, and breakthrough SARS-CoV-2 infection or COVID-19.

Per participant receiving 1 vaccine dose only (dose 3) (Group A3), the study duration will be approximately 12 months, which includes 1 week for screening, 1 day for dosing, and 12 months of follow-up after dose 3 to monitor for safety, immunogenicity, and breakthrough SARS-CoV-2 infection or COVID-19.

Part B – Booster Phase

Per healthy participant receiving 2 doses of mRNA-1273 in Part A (Group B5), the study duration will be approximately 10 months, which includes 1 week for screening (Day -7 to Day 1), 6 months for dosing (on Day 1, Day 29, and Day 129 for BD), and 6 months of follow-up after the BD to monitor for safety, immunogenicity, and breakthrough SARSCoV2 infection or COVID-19.

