7.6.3. Independent Cardiac Event Adjudication Committee

An independent cardiac event adjudication committee (CEAC) that includes pediatric and adult cardiologists will review suspected cases of myocarditis and pericarditis to determine if they meet CDC criteria of “probable” or “confirmed” events, and to assess severity ([Gargano et al 2021](#)). Any cases that the CEAC assesses as representing probable or confirmed cases of myocarditis or pericarditis will be referred to the Sponsor, which will then make a final decision on whether to suspend further enrollment and/or study dosing based on assessment of the overall potential risk to study participants or potential study participants.

The CEAC will operate under the rules of an approved charter that will be written and reviewed at the organizational meeting of the CEAC. Details regarding the CEAC composition, responsibilities, procedures, and frequency of data review will be defined in its charter.

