10.2.16. Study and Site Closure

If the study is prematurely terminated or suspended, the Sponsor shall promptly inform the investigators, the IRBs, the regulatory authorities, and any CRO(s) used in the study of the reason for termination or suspension, as specified by the applicable regulatory requirements. The investigator shall promptly inform the participants and should ensure appropriate participant therapy and/or follow-up.

The Sponsor or designee reserves the right to close the study site or terminate the study at any time for any reason at the sole discretion of the Sponsor.

The investigator may initiate study site closure at any time, provided there is reasonable cause and sufficient notice is given in advance of the intended termination.

Reasons for the early closure of a study site by the Sponsor or investigator may include, but are not limited to:

- Continuation of the study represents a significant medical risk to participants

- Failure of the investigator to comply with the protocol, the requirements of the IRB or local health authorities, the Sponsor's procedures, or GCP guidelines
- Inadequate recruitment of participants by the investigator
- Discontinuation of further mRNA-1273 development

Study sites will be closed upon study completion. A study site is considered closed when all required documents and study supplies have been collected and a study site closure visit has been performed.

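### The Section 7.6.2 pause criteria name only third-dose vaccination for suspension and lapse at the last third dose, so Part B has no pre-stated trigger to hold boosters

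*Protocol*

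**What the plan says.** Protocol Section 7.6.2 has four pause criteria: two related Grade 4 solicited reactions; five transplant recipients with a related severe systemic allergic reaction; three related SAEs or Grade 4 adverse events; and one related death. The rules "will only remain in effect until all study participants who consented to receive a third dose have received their third dose of vaccine". When a criterion is met, "vaccination with third dose may be temporarily suspended" while the Sponsor carries out an expedited review. The section does not mention Part B, the booster or any B group.

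The same section gives the Internal Safety Team (IST) two counted reviews, at 10 and at 55 transplant recipients, plus ad hoc review of any other safety concern. Both counts are of third doses. The synopsis ties them to Part A groups: "At least 55 SOT recipients have received their third dose of study vaccine (Group A2 and Group A3), unless a safety event requires earlier review".

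The neighbouring Section 7.6.1 does reach the booster phase: "In Part B, the investigator will review laboratory safety assessments of kidney and liver function". Safety of the 100 µg booster is a primary Part B objective in Table 1. Section 5.1 defines the study vaccine to include the booster.

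**The concern.** Booster recipients are dosed under a section whose stop-and-look rules were written for dose 3. Followed as written, the rules do not hold a booster at any time. Once the last consenting participant has had dose 3, they also stop prompting expedited review of booster events.

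The events left without a prompt are serious ones. Section 1.3.2 says it is not known whether the adverse events of a fourth mRNA-1273 dose differ from those of two or three. That applies to B2, B3 and those B4 participants whose outside series was three Moderna doses. B4 participants with another series and healthy B5 participants are also uncovered, although theirs is not a fourth mRNA-1273 dose. Section 1.2.2 reports the 100 µg booster as generally well tolerated in 305 recipients, with a tendency to more solicited reactions than the authorized 50 µg booster. Section 3.1 also lets Part B move to a variant-specific product, and the same gap would apply to it.

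**Working it through.** The plan states no figure on this point, so the check is mainly of the text.

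1. **Before the lapse.** The criteria count events related to the vaccine and do not say which dose must precede them. Under Section 5.1 the vaccine includes the booster, so a booster event can be read as counting and as prompting expedited Sponsor review. The stated hold still applies to third doses only.

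2. **After the lapse.** No criterion is in force, so none prompts either a hold or an expedited review.

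3. **Some boosters must fall after the lapse.** Part B inclusion requires at least 4 months since the last dose. Table 10 gives nominal days: for B2, 205 − 85 = 120 days after dose 3; for B3, 120 − 1 = 119 days. Whoever receives the last third dose and accepts a booster is therefore boosted after the rules end. The share of all boosters given after the lapse cannot be derived: Amendment 4 still enrols third-dose participants, and accrual and uptake are not stated.

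4. **Other routes to a dosing decision, by event.**
   - Organ rejection: Section 7.6.1, after committee adjudication, "The Sponsor will then make a final decision on whether to suspend further enrollment and/or study dosing".
   - Myocarditis or pericarditis: Section 7.6.3 refers probable or confirmed cases to the Sponsor, "which will then make a final decision on whether to suspend further enrollment and/or study dosing".
   - Related death, severe allergic reaction, other related SAEs, Grade 4 events: no committee route ending in a dosing decision.

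5. **Count.** Criteria naming booster dosing for suspension: 0 of 4. Counted IST reviews in the protocol that include booster recipients: 0 of 2.

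6. **How often the existing counts might be reached (illustration).** The documents give no event rates, so assume a true rate p of 1% to 3%, with at most one event per recipient. Use the planned minimum of 50 B4 recipients with a non-Moderna series. P(at least k) = 1 − Σ over j < k of C(50, j) p^j (1 − p)^(50 − j).
   - k = 2: 0.09 at 1%, 0.44 at 3%.
   - k = 3: 0.01 at 1%, 0.19 at 3%.

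   At these rates, reaching a threshold is possible but not routine.

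7. **What two booster reviews would detect.** The true rate that gives a 95% chance of at least one event among n is 1 − 0.05^(1/n). For n = 10 this is 25.9%; for n = 55 it is 5.3%. These figures describe the proposed reviews, not the defect. They concern seeing one event, whereas three of the four criteria need 2, 3 or 5.

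**The case against.** The strongest reply is that Part B is not unsupervised. The rejection and cardiac committees can lead to suspension of all study dosing. The IST can meet ad hoc for any dose. Protocol Section 8.4.1 and SAP Section 6.7 plan an interim safety analysis at booster Day 29. Section 7 sends immediate safety concerns straight to the Sponsor, and SAEs and AESIs are reported within 24 hours. The Sponsor "reserves the right to close the study site or terminate the study at any time for any reason". The existing rule itself says only that dosing may be suspended. All of this stands, and it limits the point to the missing prompt.

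A reader might go further in four ways that the documents do not support:

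- **That Part B has no safety oversight.** The routes above show otherwise, although SAP Section 6.8 confirms there is no Data Safety Monitoring Board.
- **That a booster event can never prompt expedited review.** Before the lapse, Section 5.1 allows it to count.
- **That the IST will not review boosters.** Its charter sets the frequency of review and is not among the documents. The 0 of 2 describes the protocol only.
- **That the Amendment 4 list of changed sections proves an oversight because it omits 7.6.2.** That table covers major changes, and Sections 5.1 and 7.5.6 carry Part B text without being in its Part B list. The evidence is the wording of 7.6.2 itself.

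The remaining routes do not close the gap. Ad hoc review has no threshold. Expedited reporting delivers information without setting an action. Withholding further doses under Section 6.2 concerns one participant and is not a study pause.

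**Conclusion.** The point holds in this form. Section 7.6.2 never gives a pre-stated trigger to hold booster dosing, and after the last third dose it prompts no expedited review of related booster deaths, severe allergic reactions, SAEs or Grade 4 events. The first part holds at any accrual, because the only dosing named for suspension is the third dose. How many boosters fall after the lapse is unknown.

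Those affected are at least 50 B4 recipients with a non-Moderna series, the other B4 participants, and those in A2, A3 and A5 who accept a booster. Table 2 gives A1 no booster. The conclusion rests on the protocol text alone. The charter could supply the IST reviews, but the protocol's own pause rules would still leave boosters out. This should be corrected. It takes away a prompt and leaves the Sponsor's power to stop intact.

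**What to change.** Amend Section 7.6.2 as follows:

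- (a) Keep the four criteria in force until the last booster dose has been given.
- (b) Extend the named action to third-dose or booster vaccination. State that related events after a booster count toward the criteria. Restart the booster count after each completed expedited review, so that events already reviewed do not hold boosters again.
- (c) Unless the IST charter already provides for it, add IST reviews after 10 transplant booster recipients with at least 7 days of reactogenicity data and after 55 transplant booster recipients (B2 to B4). Match this in the synopsis.

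The criteria, the 24-hour electronic reporting route and the IST already exist. The cost is protocol wording, charter wording where needed, two IST meetings and the chance that booster dosing is held briefly for review.
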